## **15.5 Study Records Retention**

Study records and reports, including, but not limited to, eCRFs, source documents, ICFs, and study drug disposition records shall be maintained for 2 years after a marketing application is approved for the drug for the indication for which it is being investigated; or, if no application is to be filed or if the application is not approved for the drug, until 2 years after the investigation is discontinued and the FDA has been notified. These documents will be retained for a longer period, however, if required by local regulations. ICFs for future research use will be maintained as long as the sample/specimen exists.

No records will be destroyed without the written consent of the sponsor. It is the responsibility of the sponsor to inform the site PI when these documents no longer need to be retained. The participating VTEU sites must contact DMID for authorization prior to the destruction of any study records.

## **15.6 Protocol Deviations**

A protocol deviation is any noncompliance with the study protocol, GCP or protocol-specific MOP requirements. The noncompliance may be either on the part of the subject, the site PI or other study personnel. As a result of protocol deviations, corrective actions are to be developed by the site and implemented promptly.

These practices are consistent with ICH E6 GCP guidelines:

- 4.5 Compliance with Protocol, Sections 4.5.1, 4.5.2 and 4.5.3
- 5.1 Quality Assurance and Quality Control, Section 5.1.1
- 5.20 Noncompliance, Sections 5.20.1 and 5.20.2

It is the responsibility of the site PI and other study personnel to use continuous vigilance to identify and report protocol deviations within five working days of identification of the protocol deviation, or within five working days of the scheduled protocol-required activity. Protocol deviations must be promptly reported to DMID, via the SDCC's Advantage eClinicalSM.

Protocol deviations, as defined above, must be addressed on the appropriate DCF. A completed copy of the Protocol Deviation DCF must be maintained in the regulatory file as well as in the subject's chart. Protocol deviations must be sent to the IRB in accordance with IRB requirements. The site PI and other study personnel are responsible for knowing and adhering to IRB requirements.

## 16 PUBLICATION POLICY

All investigators funded by the NIH must submit or have submitted for them to the National Library of Medicine's PubMed Central (<http://www.ncbi.nlm.nih.gov/pmc/>) an electronic version of their final, peer-reviewed manuscripts upon acceptance for publication, to be made publicly available no later than 12 months after the official date of publication. The NIH Public Access Policy ensures the public has access to the published results of NIH funded research. It requires all investigators to submit final peer-reviewed journal manuscripts that arise from NIH funds to the digital archive PubMed Central upon acceptance for publication. Further, the policy stipulates that these papers must be accessible to the public on PubMed Central no later than 12 months after publication.

Refer to:

- NIH Public Access Policy, <http://publicaccess.nih.gov/>
- NIH Office of Extramural Research (OER) Grants and Funding, <http://grants.nih.gov/grants/oer.htm>

As of January 2018, all clinical trials supported by the NIH must be registered on ClinicalTrials.gov, no later than 21 days after the enrollment of the first subject. Results of all clinical trials supported by the NIH, generally, need to be submitted no later than 12 months following the primary completion date. A delay of up to 2 years is available for trials that meet certain criteria and have applied for certification of delayed posting.

As part of the result posting a copy of this protocol (and its amendments) and a copy of the Statistical Analysis Plan will be posted on ClinicalTrials.gov.

For this clinical trial, the responsible party is DMID which will register this trial and post results. The responsible party does not plan to request certification of delayed posting.

Refer to:

- Public Law 110-85, Section 801, Clinical Trial Databases
- 42CFR11
- NIH NOT-OD-16-149

## **18 APPENDICES**

[Appendix A: Schedule of Study Procedures and Evaluations](#)

[Appendix B: Adverse Events of Special Interest](#)

## APPENDIX A. SCHEDULE OF STUDY PROCEDURES AND EVALUATIONS

**Table 13: Schedule of Study Procedures and Evaluations**

Study Visit Number	V00	V01	V02	V03	V04	V05	V06	V07	V08	V09	Early Termination	Unscheduled
Screening, Enrollment/Study Day and post first study vaccination	Screening D-28 to -1	Enrollment D1	D2+1d	D8+/-1d	D29+/-2d	D57+/-3d	D90+/-14d	Day118+/-3d	D180 +/-14d	D365 -14/+35		
Informed Consent o	X o											
Demographic Information	X											
Eligibility Criteria	X	X † 1										
Medical History @	X	X † 1	X	X	X	X	X	X	X	X	X	X
Concomitant Medications	X	X † 1	X	X	X						X 	X 
Vital Signs (Oral Temperature % , Pulse and BP)	X	X 									X	X
Height and Weight	X											
Physical Examination	X 	{X}	{X}	{X}	{X}	{X}	{X}	{X}	{X}	{X}	{X}	{X}
Urine or Serum Pregnancy Test	X ^	X † ^										
Venous Blood Collection for Screening Laboratories	X ≠											
Enrollment in Advantage eClinical SM and Randomization		X †										
Venous Blood Collection for Clinical Safety Laboratory Evaluations ~		X † ~		X ~							X 	X
Venous Blood Collection for Serological Assays		X †		X	X	X	X †	X	X	X	X	X
Venous Blood Collection for Cellular Immunology Assays		X †		X	X		X †				X 	
Venous Blood Collection for Transcriptomics		X †	X	X							X 	
Pre-Administration Reactogenicity Assessments		X †										

Study Visit Number	V00	V01	V02	V03	V04	V05	V06	V07	V08	V09	Early Termination	Unscheduled
Screening, Enrollment/Study Day and post first study vaccination	Screening D-28 to -1	Enrollment D1	D2+1d	D8+/-1d	D29+/-2d	D57+/-3d	D90+/-14d	Day118+/-3d	D180 +/-14d	D365 -14/+35		
Study Vaccination		X					X*					
20-minute Evaluation After Study Vaccination		X										
Examine Study Vaccination Site		X	X	X							X 	X 
Post-Administration Reactogenicity Assessments		X									X 	X 
Distribute Memory Aid and Study-Related Materials		X										
Review Memory Aid			X	X							X 	X 
AE/SAE Assessment		X &.3	X &.3	X &.3	X 	X	X 	X 	X 	X 	X 	X 

∞ Prior to study procedures.

– Review/confirm information or activity in subjects previously consented and screened.

† Prior to study vaccination.

1 Review results of ESR and clinical safety laboratory evaluations.

@ Complete medical history (including solicitation for receipt of any non-study influenza vaccine) will be obtained by interview of subjects at the screening visit and interim medical history will be obtained by interview of subjects on Day 1 prior to study vaccination and at follow-up visits after study vaccination.

\$ Vital signs assessed on Day 1 prior to the study vaccination will be considered as baseline.

% Subjects must not eat or drink anything hot or cold, or smoke within 10 minutes prior to taking oral temperature.

2 At the screening visit a physical examination will be performed on all subjects to include the following organs and organ systems: skin, head and neck, lungs, heart, liver, spleen, extremities, lymph nodes, and nervous system.

{ } Targeted physical examination if indicated based on review of interim medical history.

^ Performed locally by the site at the screening visit (optional); Must be performed within 24 hours prior to study vaccination for all women of childbearing potential. Results must be negative and known prior to randomization on Day 1 and administration of study vaccination.

≠ ESR Performed by local laboratory, WBC, Hgb, PLT, ALT, T. Bili, AST, GGT, ALP, serum lipase, serum amylase and Cr will be sent to the central clinical laboratory.

~ Includes, WBC, Hgb, PLT, ALT, T. Bili, AST, GGT, ALP, serum lipase, serum amylase and Cr.

& Inclusive of reactogenicity assessments performed on the day of study vaccination through 7 days after study vaccination.

 AEs (if visit occurs on or before Day 29), SAEs, AESIs (including Protocol Specified AESIs, MAAEs, NOCMCs and PIMMCs), for subjects who are being followed for safety.

 SAEs and AESIs (including Protocol Specified AESIs, MAAEs, NOCMCs and PIMMCs), for subjects who are being followed for safety.

 Investigators have the discretion of administering 2019/2020 Fluzone or Flublok earlier than the Day 90 window (i.e earlier than Day 76) if 10% of more of surveillance samples in the CDC geographic region surrounding the local site test positive for influenza.

If within 365 after first study vaccination

 If within the first 7 days after the first study vaccination

 If prior to or at the D90 visit

 If prior to or at the D8 visit

\* Seasonal QIV 2019/2020

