**Table 1: Study Objectives and Outcome Measures**

Primary Safety Objectives	Primary Safety Outcome Measures

 
To assess the safety and reactogenicity of 2018/2019 Fluzone and Flublok with and without AF03 or Advax-CpG55.2 adjuvant.
 
	
 
Occurrence of solicited injection site and systemic reactogenicity events through approximately Day 8 after the first study vaccination.
 
Occurrence of unsolicited adverse events from the time of the first study vaccination through approximately Day 29.
 
Occurrence of all SAEs through approximately 12 months following receipt of the first study vaccination.
 
Occurrence of abnormal clinical safety laboratory AEs from the time of study vaccination through approximately Day 8 after the first study vaccination.
 

Primary Immunogenicity Objectives	Primary Immunogenicity Outcome Measures

 
To assess the serum hemagglutination inhibition (HAI) antibody responses against 2018/2019 QIV strains from baseline (Day 1) to approximately Day 29 after receipt of 2018/2019 Fluzone and Flublok with and without AF03 or Advax-CpG55.2 adjuvant.
 
	
 
The percentage of subjects achieving HAI titer seroconversion against the 2018/2019 QIV strains (defined as either a pre-vaccination titer <1:10 and a post-vaccination titer ≥1:40 or a pre-vaccination titer ≥1:10 and a minimum four-fold rise in post-vaccination antibody titer) on approximately Day 29 for each study group.
 
The percentage of subjects with an HAI titer ≥1:40 against the 2018/2019 QIV strains at baseline and approximately Day 29 for each study group.
 
Geometric mean titers (GMTs) of serum HAI against the 2018/2019 QIV strains at baseline and approximately Day 29 for each study group.
 

	
 
• Ratio of GMTs of serum HAI against the 2018/2019 QIV strains between adjuvanted and unadjuvanted study groups at baseline and approximately Day 29.
 
• Geometric mean fold rise (GMFR) in HAI titers from baseline (Day 1) against the 2018/2019 QIV strains at approximately Day 29 for each study group
 

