### **8.2.2 Visit 03, Day 8, Clinic Visit**

#### **(Window: Day 8 +/- 1 day post study vaccination)**

- Interim medical history, including an assessment for new medical conditions, stability of chronic diseases and symptoms suggestive of AESIs (including Protocol Specified AESIs, MAAEs, NOCMCs and PIMMCs), will be obtained by interview of subjects and any changes since the previous clinic visit will be noted.
- All concomitant medications (including solicitation for receipt of any non-study influenza vaccines) will be recorded on the appropriate DCF.
- All AE/SAEs will be recorded on the appropriate DCF.
- Memory Aid information will be reviewed with subjects.
- A targeted physical examination, including an assessment for signs suggestive of AESIs (including Protocol Specified AESIs, MAAEs, NOCMCs and PIMMCs), may be performed, if indicated based on review of interim medical history, by a study clinician licensed to make medical diagnoses and listed on the Form FDA 1572 as the site PI or sub-investigator.

- The study vaccination site will be examined.
- Counsel on avoidance of pregnancy.
- Approximately 6mL of venous blood will be collected for clinical safety labs (WBC, Hgb, PLT, ALT, T. Bili, AST, GGT, ALP, serum lipase and amylase and Cr) to be performed by the Central Clinical Laboratory.
- Approximately 20 mL of venous blood will be collected for serological assays.
- Approximately 48 mL of venous blood will be collected for cellular immunology assays.
- Approximately 3 mL of venous blood will be collected for transcriptomic analyses.

Note: Subjects that complete this visit on Day 7 will be reminded to complete their Memory Aid through the end of Day 8, and study personnel will contact these subjects by phone to review their Memory Aid information and solicit any AE/SAEs and concomitant medications (including solicitation for receipt of any non-study influenza vaccines).

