### **8.2.3 Visit 04, Day 29, Clinic Visit**

#### **(Window: Day 29, +/-2 days post study vaccination)**

- Interim medical history, including an assessment for new medical conditions, stability of chronic diseases and symptoms suggestive of AESIs (including Protocol Specified AESIs, MAAEs, NOCMCs and PIMMCs), will be obtained by interview of subjects and any changes since the previous clinic visit will be noted.
- All concomitant medications (including solicitation for receipt of any non-study influenza vaccines) will be recorded on the appropriate DCF.
- All AE/SAEs will be recorded on the appropriate DCF.
- A targeted physical examination, including an assessment for signs suggestive of AESIs (including Protocol Specified AESIs, MAAEs, NOCMCs and PIMMCs), may be performed, if indicated based on review of interim medical history, by a study clinician licensed to make medical diagnoses and listed on the Form FDA 1572 as the site PI or sub-investigator.
- Counsel on avoidance of pregnancy.

- Approximately 20 mL of venous blood will be collected for serological assays.
- Approximately 80 mL of venous blood will be collected for cellular immunology assays.

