#### **8.2.4 Visit 05, Day 57, Clinic Visit**

##### **(Window: Day 57 +/- 3 days post study vaccination)**

- Interim medical history, including an assessment for new medical conditions, stability of chronic diseases and symptoms suggestive of AESIs (including Protocol Specified AESIs, MAAEs, NOCMCs and PIMMCs), will be obtained by interview of subjects and any changes since the previous clinic visit will be noted.
- Receipt of any non-study influenza vaccines will be recorded on the appropriate DCF.
- SAEs, AESIs (including Protocol Specified AESIs, MAAEs, NOCMCs and PIMMCs) will be recorded on the appropriate DCF.
- A targeted physical examination, including an assessment for signs suggestive of AESIs (including Protocol Specified AESIs, MAAEs, NOCMCs and PIMMCs), may be performed, if indicated based on review of interim medical history, by a study clinician licensed to make medical diagnoses and listed on the Form FDA 1572 as the site PI or sub-investigator.
- Counsel on avoidance of pregnancy.
- Approximately 20 mL of venous blood will be for serological assays.

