## **9 ASSESSMENT OF SAFETY**

### **9.1 Specification of Safety Parameters**

Safety will be assessed by the frequency and severity of:

1. SAEs occurring from the time of the first study vaccination through approximately 12 months after the first study vaccination.
2. Solicited AEs – reactogenicity events occurring from the time of the first study vaccination through 7 days after the first study vaccination:
  - a) Injection site reactions including pruritus, ecchymosis, erythema, induration, edema, pain, and tenderness.
  - b) Systemic reactions including fever, feverishness, fatigue, malaise, myalgia, arthralgia, headache, and nausea.
3. Clinical safety laboratory AEs occurring from the time of the first study vaccination through approximately 7 days after the first study vaccination. Parameters to be evaluated include WBC, Hgb, PLT, ALT, T. Bili, AST, GGT, ALP, serum lipase, serum amylase, and Cr.
4. Unsolicited AEs –non-serious AEs occurring from the time of the first study vaccination through approximately Day 29.
5. AESIs (including Protocol Specified AESIs, MAAEs, NOCMCs and PIMMCs) occurring from the time of the study vaccination through approximately 12 months after the first study vaccination.

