 @ Complete medical history (including solicitation for receipt of any non-study influenza vaccine) will be obtained by interview of subjects at the screening visit and interim medical history will be obtained by interview of subjects on Day 1 prior to study vaccination and at follow-up visits after study vaccination.
 § Vital signs assessed on Day 1 prior to the study vaccination will be considered as baseline.
 % Subjects must not eat or drink anything hot or cold, or smoke within 10 minutes prior to taking oral temperature.
 2 At the screening visit a physical examination will be performed on all subjects to include the following organs and organ systems: skin, head and neck, lungs, heart, liver, spleen, extremities, lymph nodes, and nervous system.
 {} Targeted physical examination if indicated based on review of interim medical history.
 ^ Performed locally by the site at the screening visit (optional); Must be performed within 24 hours prior to study vaccination for all women of childbearing potential. Results must be negative and known prior to randomization on Day 1 and administration of study vaccination.
 ≠ ESR Performed by local laboratory, WBC, Hgb, PLT, ALT, T. Bili, AST, GGT, ALP, serum lipase, serum amylase and Cr will be sent to the central clinical laboratory.
 ~ Includes, WBC, Hgb, PLT, ALT, T. Bili, AST, GGT, ALP, serum lipase, serum amylase and Cr.
 & Inclusive of reactogenicity assessments performed on the day of study vaccination through 7 days after study vaccination.
³ AEs (if visit occurs on or before Day 29), SAEs, AESIs (including Protocol Specified AESIs, MAAEs, NOCMCs and PIMMCs), for subjects who are being followed for safety.
⁴ SAEs and AESIs (including Protocol Specified AESIs, MAAEs, NOCMCs and PIMMCs), for subjects who are being followed for safety.
⁵ Investigators have the discretion of administering 2019/2020 Fluzone or Flublok earlier than the Day 90 window (i.e. earlier than Day 76) if 10% or more of surveillance samples in the CDC geographic region surrounding the local site test positive for influenza.
⁶ If within 365 after first study vaccination
⁷ If within the first 7 days after the first study vaccination
⁸ If prior to or at the D90 visit
⁹ If prior to or at the D8 visit
 * Seasonal QIV 2019/2020

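### Footnote 3 of the schedule ties AE collection to the visit date, so at an in-window Visit 04 on Day 30 or 31 the table contradicts the visit text and the primary safety outcome

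*Protocol*

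**What the plan says.** Table 13 in Protocol Appendix A attaches footnote 3 to the AE/SAE Assessment cell at Visits 01 to 04 and at Early Termination and Unscheduled visits. It asks for "AEs (if visit occurs on or before Day 29), SAEs, AESIs (including Protocol Specified AESIs, MAAEs, NOCMCs and PIMMCs". Only the general AE item carries the date condition; SAEs and the special-interest categories are collected at any date. SAP Table 2 has the same footnote: "AEs (if visit occurs on or before Day 29".

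The body of the protocol reads differently:

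- Section 8.2.3 sets the Visit 04 window as "Window: Day 29, +/-2 days post study vaccination" and instructs that "All AE/SAEs will be recorded on the appropriate DCF". No date limit is attached.
- Section 8.2.2 sets the preceding visit, Visit 03, as "Window: Day 8 +/- 1 day post study vaccination".
- Section 8.2.4 (Visit 05, Day 57) says "SAEs, AESIs (including Protocol Specified AESIs, MAAEs, NOCMCs and PIMMCs) will be recorded on the appropriate DCF". In Table 13 the Visit 05 cell is a plain X with no footnote; footnote 4, which restricts collection to SAEs and AESIs, starts at Visit 06.
- Sections 8.4 and 8.5 (Early Termination and Unscheduled visits) include unsolicited AEs if they arose within 28 days of the first vaccination.
- Table 1 gives as a primary safety outcome "Occurrence of unsolicited adverse events from the time of the first study vaccination through approximately Day 29". Section 9.1 likewise lists "non-serious AEs occurring from the time of the first study vaccination through approximately Day 29".

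SAP Section 9.3.2 takes the total safety population as the denominator for unsolicited AE incidence.

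**The concern.** The footnote conditions on the wrong variable. What decides whether an AE belongs to the outcome is when it began; the footnote asks when the subject came to the clinic. A subject seen on Day 30 or 31 is on schedule, yet the table tells the site to leave out ordinary unsolicited AEs at that visit, while Section 8.2.3 tells it to record them all. Two operative instructions for a primary safety outcome disagree on days the protocol permits.

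If a site works from the table, the gap covers most of the period after Visit 03, and the analysis cannot see it. With the whole safety population as denominator, a subject who was not asked looks the same as a subject with no event. The SAP plans summaries for Days 1-29 and, separately, Days 9-29, and the second would be the more exposed. Section 2.1 states that this is the first human use of an Advax-CpG formulation containing CpG55.2, so under-ascertainment is unwelcome here.

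**Working it through.** The plan gives no figure on this point to reproduce. The check is window arithmetic and a comparison of the rules.

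**1. Permitted Visit 04 days.** 29 - 2 = 27 to 29 + 2 = 31, that is Days 27, 28, 29, 30 and 31. Days 30 and 31 fail the footnote's condition: 2 of 5. These are permitted days, not a share of subjects.

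**2. Where the condition has any effect.** Visit 03 ends at 8 + 1 = Day 9, so Visits 01 to 03 always satisfy it. It can bite only at Visit 04, Early Termination and Unscheduled visits.

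**3. Span exposed at a Day 30 or 31 visit.** The last scheduled AE assessment is Visit 03 on Day 7, 8 or 9, so the first uncovered day is 8, 9 or 10:

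- from Day 8: 29 - 8 + 1 = 22 days
- from Day 9: 29 - 9 + 1 = 21 days
- from Day 10: 29 - 10 + 1 = 20 days

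That is 20 to 22 of the 29 days. Section 8.2.2 adds a phone contact for Day 7 attenders that covers them through Day 8, which brings their 22 days down to 21.

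**4. What is omitted.** Under the footnote, SAEs, AESIs, MAAEs, NOCMCs and PIMMCs are still collected, and Section 9.2.1 allows an AESI to be non-serious. Only non-serious AEs outside those categories are exposed. Section 9.2.1 does identify MAAEs by asking about medical attention for each unsolicited AE, so dropping the general question could also weaken MAAE capture.

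**5. Rules side by side.**

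| Place | Collection depends on |
|---|---|
| Table 13 and SAP Table 2, footnote 3 | date of the visit |
| Section 8.2.3, Visit 04 | nothing; all AEs recorded |
| Sections 8.4 and 8.5 | AE arising within 28 days, that is by Day 1 + 28 = Day 29 |
| Table 1 and Section 9.1 | AE occurring through approximately Day 29 |

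The footnote is the only one that turns on the visit date, and at each of the three visit types where it can act, the body text differs from it.

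**6. Recovery at Visit 05.** The text limits that visit to SAEs and AESIs. The bare X in the table sets no limit, but it also does not say that AEs with onset by Day 29 are to be picked up there. Neither source assures recovery.

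**The case against.** The strongest reply is that a loss appears only by taking Visit 04 from the table and Visit 05 from the text. A site that follows the text throughout records all AEs at Visit 04. A site that follows the table throughout meets an unrestricted X at Visit 05. The event-based rule also appears repeatedly in Section 9, and Section 9.2.5 makes the investigator responsible for recording all AEs observed or reported. On this view footnote 3 is a wording slip, perhaps shorthand for the Day 29 visit, and the outcome itself says approximately Day 29.

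Much of this stands. The documents show a contradiction that permits loss; they do not show that loss occurs. The word approximately softens the clash with the outcome, though not the clash with Section 8.2.3. The shorthand reading is possible, but footnotes 8 and 9 of the same table name a visit when a visit is meant, and footnote 3 names a day. The bare X at Visit 05 is weak protection, because the text for that visit says otherwise.

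A reader might also infer that subjects who miss Visit 04 and return at an Early Termination or Unscheduled visit certainly lose these AEs. That is not supported: Sections 8.4 and 8.5 already go by when the AE arose, so there too the finding is a conflict between table and text.

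**Conclusion.** The point holds as an internal contradiction in an operative rule for a primary safety outcome. At an in-window Visit 04 on Day 30 or 31, footnote 3 read literally omits non-serious unsolicited AEs outside the AESI, MAAE, NOCMC and PIMMC categories for about 20 to 22 days. The visit text, Section 9.1 and the outcome definition all require them. Recovery at Visit 05 is not assured, and any loss would lower the reported incidence. The documents give no reason to expect the loss to differ between arms, since subjects and assessors are blinded.

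The size of any loss cannot be derived. Two stronger readings should be resisted:

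- A reader might turn 2 of 5 days into 40% of subjects (0.40 x 240 = 96). That assumes visits spread evenly over the window and every site letting the table override Section 8.2.3. The documents give neither, nor an expected AE incidence from which to compute a biased rate.
- A reader might conclude that no non-serious AEs are collected after Day 29. The footnote itself keeps the special-interest categories, which can be non-serious.

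No sample size, power or precision figure in the plan is affected.

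**What to change.** In Protocol Table 13 and SAP Table 2, reword the AE part of footnote 3 along these lines: *AEs with onset through approximately Day 29, whatever the date of the visit*. This brings the table into line with Sections 8.2.3, 8.4, 8.5 and 9.1.

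Then reconcile the Visit 05 cell with Section 8.2.4 by giving the cell a footnote and adding a line to the visit text, so that AEs with onset in that period are recorded at the next contact if Visit 04 was missed.

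The cost is one footnote in each document, plus one cell note and one sentence for Visit 05. No visit, sample or extra contact is added. In particular, Day 27 or 28 attenders need no further call, since those days are in window and the outcome runs only to approximately Day 29.
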